8.1.7 Long Term Observation Period (Visits 24 – 28; 28 ± 4 days)

[Purpose] To evaluate safety and observe wound status

No further applications of TTAX01 are permitted beyond Visit 16. Subjects enter this Long Term Observation Period whether they have not completely healed their wound, or, they have achieved complete closure. If they have achieved complete wound closure, where healing has been confirmed at two consecutive visits each two weeks apart, but their wound re-opens during this period, it will be regarded as a failure of durable healing.

If at any Long Term Observation Visit a previously unhealed index ulcer is observed to be closed, perform the following procedures:

- Assess adverse events
- Review concomitant medications
- Assess subject compliance regarding off-loading since the last visit
- Obtain photographs of the closed ulcer using the electronic wound imaging and measuring device
- Observe the wound if it is fully epithelialized with no drainage or need for a dressing, record it as closed.

The next visit scheduled will serve as the first consecutive confirmation visit in 14 ± 2 days and will begin the confirmation of closure procedures (refer to Section 8.1.9).

Otherwise,

- Assess adverse events
- Review concomitant medications. These will be recorded in the subject's source document, but should only be recorded in the eCRF for the following:
 - All current and past treatments for the index ulcer only
 - Concomitant medications used to treat the index ulcer (e.g., systemic antibiotics for an index ulcer infection) and the peri-ulcer area (such as treatment for erythema, irritation, itching), together with the indication for the medication

- Concomitant medications used to treat all SAE, and all AE considered "RELATED" to the product will be recorded in the appropriate eCRF.
- Assess the foot and lower extremity, then assess the index ulcer after removal of the dressing.
 - Determine whether skin and soft tissue infection (SSTI) is present. If SSTI is present, without evidence of osteomyelitis, obtain a deep tissue biopsy for histopathology, culture and sensitivity, and adjust the antibiotic regimen (start a 2 week course of antibiotics if none are being taken, or revise antibiotics if still being taken for a previous infection)
 - If new, recurrent or persistent osteomyelitis is suspected, determine whether the wound probes to bone, and obtain imaging or scanning. If osteomyelitis is confirmed, start a 6 week course of antibiotics if none are being taken, or revise antibiotics if still being taken for a previous osteomyelitis.
- Clean the wound using sterile saline, non-ionic cleanser or a hypochlorous solution.
 Antiseptic agents including hydrogen peroxide, acetic acid, chlorhexidine, povidone/iodine, and cetrimide should not be used.
- The wound should be sharply debrided to remove callus, macerated, necrotic/devitalized/non-viable tissue and purulence observed on the wound edge and wound bed. Debride until the wound edge is clean and sharply defined, with at least punctate bleeding at the edge and wound bed.
- Obtain photograph and measure the area and volume of the wound using the provided electronic wound imaging and measuring device (after debridement, if performed).
- Apply wound dressing including a non-adherent, standard foam pad or alginate dressing (e.g., hydrogels, foam dressings, and alginates) that is appropriate for the amount of drainage, and a secondary bandage to ensure a moist wound environment, which adequately controls exudate and avoids maceration of the surrounding skin. Alternative therapies are allowed during this period, per Section 6.5.

- Continue with the off-loading device appropriate to the location of the ulcer (preferably with full length boot or total contact cast, unless not appropriate per the physician, in which case a substitute off-loading device can be made with sponsor approval).
- Adjust infection management including antibiotics as needed, as indicated by the results from the microbiology and histopathology bone biopsy.

Schedule the next Long Term Observation Period visit for 28 ± 4 days or, if the subject is at Visit 28, schedule the End of Study visit for 28 ± 7 days.

8.1.8 End of Study Visit (Visit 29; Day 344 ± 7)

[Purpose]: To document the patient status if they complete the entire treatment period or if they are withdrawn from the study during this period.

Begin with the following procedures:

- Assess adverse events
- Review any changes in concomitant medications
- Obtain photograph of the index ulcer using the electronic wound imaging and measuring device
- Assess the index ulcer

If at this visit a previously unhealed index ulcer is observed to be closed,

perform the following procedures:

- Assess adverse events
- Review concomitant medications
- Assess subject compliance regarding off-loading since the last visit
- Obtain photographs of the closed ulcer using the electronic wound imaging and measuring device

 Observe the wound – if it is fully epithelialized with no drainage or need for a dressing, record it as closed.

The next visit scheduled will serve as the first consecutive confirmation visit in 14 ± 2 days and will begin the confirmation of closure procedures (refer to Section 8.1.9).

Otherwise,

- Perform physical examination, including vital signs (i.e., heart and respiratory rates, blood pressure, and temperature while patient is seated)
- Perform Laboratory Assessments as listed in Table 8.1.1-1 including the pregnancy test for females of childbearing potential
- Instruct subject to complete the PROMIS Lower Extremity Function questionnaire and the CWIS.

Complete subject disposition forms and exit the subject from the study.

8.1.9 Confirmation of Closure ("C" Visits)

[Purpose:] These visits serve to confirm that a wound has achieved complete closure

Confirmation of Closure visits are used to record the initial observation of closure, and persistent closure. Ideally, a wound that shows initial closure will still be closed at a confirmation visit two weeks later, and at a second confirmation visit four weeks later. At each of the confirmatory visits, use the Confirmation of Closure visit form(s) to record observations. Continue with the off-loading device appropriate to the location of the ulcer during the period of confirmatory visits.

Perform the following procedures:

- Assess adverse events
- Review concomitant medications
- Assess subject compliance regarding off-loading since the last visit

- Obtain photographs of the ulcer using the electronic wound imaging and measuring device
- Observe the wound if it is fully epithelialized with no drainage or need for a dressing, record it as closed.

If the wound is found to be open at either confirmation visit or if the subject misses a scheduled confirmation visit, record it as such and then move directly to the original schedule of visits. This may become a treatment visit for example if the subject has not passed Visit 16, or an observation visit if the subject has passed Visit 16.

If the index ulcer is closed at the first confirmation visit, schedule the subject to return for a second consecutive confirmation visit in 14 ± 2 days. If the index ulcer remains closed at the second confirmation visit, schedule the subject to begin the Long Term Observation Period at the next study day that will put the subject onto the planned 28 day schedule of visits. For example, if a subject completes the second confirmation visit on Day 50, they should return on Day 64 and continue thereafter with visits every 28 ± 3 days. Days 92, 120, 148, 176, 204, or 232 are the other days on which these subjects can enter into Long Term Observation. Note that Day 176 has a unique window of plus or minus 2 days, otherwise these visits have windows of plus or minus 3 days.

If the initial closure is observed at Visit 28 or 29, the subject should move immediately to the End of Study procedures once both confirmation visits are completed, or if the wound is found to be open at either of the two confirmatory visits.

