8.1.4 Treatment Period (Visits 2– 16; 7 ± 2 days)

[Purpose]: To monitor safety and wound healing, adjust antibiotic regimens, and administer treatment. At each visit of Visits 2 through 16, the listed procedures will be performed for the subject based upon status of the wound.

If the subject will discontinue from TTAX01 treatment at any of these visits, the subject should continue with the scheduled visits through the end of the study in order to observe wound status and general safety. If the subject will discontinue from the trial (drop-out), move immediately to the End of Study Visit (Visit 29) and complete all of the procedures listed.

Beginning at Visit 9 (Day 57), if the wound is not \geq 50% reduced in wound area versus the post debridement measurement obtained at the Initial Procedure Visit prior to randomization, the Investigator may begin to utilize adjunctive therapies as explained in Section 6.5.

If at any Treatment Visit the index ulcer is observed to be closed, perform the following procedures:

- Assess adverse events
- Review concomitant medications
- Assess subject compliance regarding off-loading since the last visit
- Obtain photographs of the closed ulcer using the electronic wound imaging and measuring device
- Observe the wound if it is fully epithelialized with no drainage or need for a dressing, record it as closed.

The next visit scheduled will serve as the first consecutive confirmation visit in 14 ± 2 days and will begin the confirmation of closure procedures (refer to Section 8.1.9).

If the wound remains open, conduct the following procedures:

- Assess adverse events
- Review concomitant medications. These will be recorded in the subject's source document, but should only be recorded in the eCRF for the following:
 - All current and past treatments for the index ulcer only
 - Concomitant medications used to treat the index ulcer (e.g., systemic antibiotics for an index ulcer infection) and the peri-ulcer area (such as treatment for erythema, irritation, itching), together with the indication for the medication
 - Concomitant medications used to treat all SAE, and all AE considered "RELATED" to the product will be recorded in the appropriate eCRF.
- Assess subject compliance regarding off-loading since the last visit
- Assess the foot and lower extremity, then assess the index ulcer after removal of the dressing (but do not remove residual TTAX01 in the treatment group).

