8.1.11 Early Termination Visit

If a subject is withdrawn from their randomized treatment for any reason, they should be encouraged to continue with the subsequent scheduled visits for observation. The Observational Period visits are particularly valuable in monitoring long-term adverse events, (e.g., unresolved ongoing adverse events, and new treatment related adverse events including limb amputation for ulcers that do not heal).

If a subject is being withdrawn from the trial, attempt to schedule an early termination visit at which the End of Study procedures are carried out (refer to Section 8.1.6). Complete procedures described therein and document the reason for the subject's withdrawal.

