9.4.3 Analysis of the Secondary Endpoints

Secondary efficacy endpoints in this study include proportions of index ulcer healed by Week 50, proportions of wound re-ulcerations by Week 50, proportions of minor and major amputations by Week 50, and total score of PROMIS Lower Extremity Function Questionnaire at end of study.

The non-parametric Cochran-Mantel-Haenszel (CMH) test with adjustment for baseline wound size cohort will be used to examine treatment effects for the SC plus TTAX01 arm vs. SC alone arm on proportion of subjects with index ulcer achieving and remaining healed at Week 50, proportion of subjects (among those with complete wound healing before Week 50) with wound re-ulceration at Week 50, and proportion of subjects with minor and/or major amputations by Week 50. Subjects' missing values at Week 50 in these endpoints, due to either no assessment or early termination from the study, will be imputed using the last-observation carry forward (LOCF).

An analysis of covariance model (ANCOVA) with treatment and baseline wound size as effect will be used to analyze total score of PROMIS Lower Extremity Function Questionnaire at end of study. Subjects' missing values in this endpoint, due to either no assessment or early termination from the study, will utilize the assessment collected at the early termination visit.

The analyses of the secondary efficacy endpoints will be performed for the ITT population and PP population as well as the LO population.

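### For ulcers first seen closed at Visit 28 or 29, the End of Study assessments fall anywhere from Day 330 to Day 372 depending on what the wound does next, and the early exit contradicts other protocol rules

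*Protocol*

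**What the plan says.** - **End of Study visit.** The heading "8.1.8 End of Study Visit (Visit 29; Day 344 ± 7") fixes the day and window. All subjects first have adverse events, medications, a photograph and an ulcer assessment. The text then branches. An ulcer newly seen closed goes to confirmation visits. Only the other branch contains the physical examination, the laboratory tests and the instruction "Instruct subject to complete the PROMIS Lower Extremity Function questionnaire and the CWIS".
- **Schedule of Activities (1.3).** Examination, labs, PROMIS and CWIS are marked at Visit 29 without condition, and none is marked in the Confirmation column.
- **Confirmation visits (8.1.9).** The general rule is that a subject who is open at, or misses, a confirmation visit should "move directly to the original schedule of visits". The last paragraph gives a different rule for late closers, meaning those whose ulcer is first seen closed at Visit 28 or Visit 29. They "should move immediately to the End of Study procedures once both confirmation visits are completed, or if the wound is found to be open", which applies to the first and the second confirmation visit alike.
- **Completion (4.4).** A subject completes the study by completing Visit 29.
- **Planned extension (4.1).** Closure first seen at the final visit extends participation to 54 weeks.
- **Early leavers.** 8.1.11 says to "attempt to schedule an early termination visit at which the End of Study procedures are carried out (refer to Section 8.1.6"). Section 8.1.6 is the Bi-Weekly Observation Period. For a missing PROMIS score, the analysis in 9.4.3 "will utilize the assessment collected at the early termination visit"; missing Week 50 healing, re-ulceration and amputation values are filled by LOCF.

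**The concern.** PROMIS at study end and the Week 50 proportions are secondary efficacy endpoints. For late closers, the day on which PROMIS is taken depends on whether the wound closed, at which visit, and whether it stayed closed. Treatment is meant to change those same events.

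A subject who closes at Visit 28 and reopens at once leaves before Visit 29 is due, while a subject who never closed keeps Visit 29. Re-closure or amputation in the gap is not seen for the first subject and is seen for the second. Week 50 status for the first subject then rests on a value carried forward.

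The document also gives sites two rules for the same subject in 8.1.9, and two answers (8.1.8 and the Schedule of Activities) on whether PROMIS, CWIS, labs and examination are done at Visit 29.

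**Working it through.** **1. Reproduce the stated day.** "Beginning at Visit 9 (Day 57") implies randomization on Day 1, since 1 + 8 × 7 = 57.
- Visit 20: 1 + 19 × 7 = Day 134
- Visit 23: 134 + 3 × 14 = Day 176, which matches the day named in 8.1.9
- Visit 28: 176 + 5 × 28 = Day 316
- Visit 29: 8.1.7 says to "schedule the End of Study visit for 28 ± 7 days", so 316 + 28 = Day 344. The stated figure is reproduced; its window is Days 337 to 351.

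**2. End of Study day on each late-closure path.** C1 is the closure visit + 14 days and C2 is + 28 days. I assume the End of Study procedures are done at the confirmation visit that triggers them.

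| First closed at | Then | Nominal day | Against Day 344 |
|---|---|---|---|
| Visit 28 | open at C1 | 316 + 14 = 330 | 14 days early |
| Visit 28 | reaches C2 | 316 + 28 = 344 | on time |
| Visit 29 | open at C1 | 344 + 14 = 358 | 14 days late |
| Visit 29 | reaches C2 | 344 + 28 = 372 | 28 days late |

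The nominal spread is 372 − 330 = 42 days.

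Allowing visit windows around nominal days (Visit 28 ± 4, Visit 29 ± 7, each confirmation step ± 2):
- The first path runs from Day 312 + 12 = 324 to Day 320 + 16 = 336, wholly before the window opens on Day 337.
- The third runs from Day 337 + 12 = 349 to Day 351 + 16 = 367, overlapping the window only at its edge.
- The fourth runs from Day 337 + 24 = 361 to Day 351 + 32 = 383, wholly after it.

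**3. Rules side by side.** A Visit 28 closer who is open at C1 is sent by the general rule in 8.1.9 to Visit 29 on Day 344, and by its last paragraph to End of Study at about Day 330. Under 4.4, the second route is not completion. A Visit 29 closer who misses a confirmation visit is not covered by the late-closure rule, and the general rule returns that subject to a schedule with no visits left. The deferred assessments then have no assigned visit.

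**4. How many subjects.** The protocol gives no late-closure rate for this trial, so two assumptions bracket it.
- *Real-world figures in 2.2* (34.7% healed at 16 weeks, 42.5% at one year), with late closures spread evenly: (42.5 − 34.7) / 36 = 0.217 points per week. Over the 8 weeks ending at Visit 29 this is 1.7%, or about 4 of 250; about 2 of these fall at Visit 29.
- *Constant hazards* fitted to the 9.2 planning rates (40% and 65% healed, placed at Visit 23, 175 days after Day 1) and extended: daily hazard −ln(0.60)/175 = 0.00292 for control and −ln(0.35)/175 = 0.00600 for TTAX01. The proportion open at Visits 27, 28 and 29 (287, 315 and 343 days) is 0.433, 0.399, 0.367 for control and 0.179, 0.151, 0.128 for TTAX01. First closure at Visit 28 is then about 3.4% and 2.8%, and at Visit 29 about 3.1% and 2.3%. With 125 per arm, that is about 8 subjects at Visit 28 and 7 at Visit 29, 15 in all.

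Only Visit 29 closers (about 2 to 7) and those Visit 28 closers who reopen by C1 are mistimed. The protocol gives no reopening rate, so the second group is an unknown part of about 2 to 8.

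**The case against.** The strongest reply is that the protocol defers these assessments by design. Section 4.1 openly plans the extension to 54 weeks, 8.1.9 brings Visit 29 closers back to the End of Study procedures, and PROMIS is defined at study end, not on a fixed day. The late-closure sentence can be read as a specific exception to the general rule. This stands against any reading that the assessments are skipped: on the main path they are postponed. It does not explain why the Schedule of Activities marks them at Visit 29 and not at confirmation visits, or why a reopened Visit 28 closer should leave before the window opens.

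A reader might also infer that Week 50 healing data are widely compromised. They are not. Wound status in Visit 29 closers is recorded at Visit 29 before the branch, and a Visit 28 closure confirmed at C2 is on schedule.

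A reader might infer from 8.1.11 that early leavers will have no PROMIS score, and that it will be missing by outcome. The cited section indeed lists no PROMIS, CWIS, labs or examination. But the sentence itself names the End of Study procedures, and 7.2 and 8.1.4 both send early leavers to them. The intent is clear, and a wrong section number does not act by wound outcome. The planned 10% dropout (0.10 × 250 = 25 subjects) shows how many may rely on the rule in 9.4.3, not how many would lose data.

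Finally, even under constant hazards the arms differ by less than one percentage point at each visit, about one subject or fewer per arm of 125. A material treatment-related bias is not shown.

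**Conclusion.** The point holds as a set of contradictions with small numerical reach. For wounds first closed at Visit 28 or 29, the End of Study day depends on wound outcome, from nominal Day 330 to Day 372 against Day 344 ± 7; three of the four paths miss the nominal window. The Day 330 exit conflicts with the general rule in 8.1.9 and with 4.4, and loses about 14 days of wound and amputation observation before Week 50. The branch in 8.1.8 conflicts with the Schedule of Activities, and a missed confirmation visit after Visit 29 leaves the assessments without a visit. The reference in 8.1.11 is an error to correct and nothing more.

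About 4 to 15 of 250 subjects would first close at these visits, and fewer would be mistimed. That range rests on the two late-closure assumptions shown. The effect on the secondary endpoints is probably small, and the 26-week primary endpoint is untouched. The case for changing the text is that sites cannot follow all of it, and that the repair is cheap.

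**What to change.** - **8.1.8:** collect PROMIS and CWIS, with the examination and labs as in the Schedule of Activities, at Visit 29 whatever the wound status. Use any later visits only to confirm closure. This also removes the gap after a missed confirmation visit.
- **8.1.9:** reconcile the late-closure rule with the general rule and with 4.4, so that a subject first closed at Visit 28 keeps the Week 50 assessment at Day 344 ± 7 even if open at C1.
- **8.1.11:** change the reference from 8.1.6 to 8.1.8.

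The cost is a few sentences in an amendment. No procedure is added: the assessments move to a visit that already takes place, and a few subjects keep a Visit 29 they would otherwise lose. One small downside is that, for Visit 29 closers, the final labs and examination would precede about four weeks of confirmation follow-up; adverse events are still assessed at those visits.

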8.1.10 Unscheduled Visits

Unscheduled exams may be conducted at the discretion of the Investigator. All obtained information should be recorded in the source documents and on the Unscheduled Visit CRF.

8.1.11 Early Termination Visit

If a subject is withdrawn from their randomized treatment for any reason, they should be encouraged to continue with the subsequent scheduled visits for observation. The Observational Period visits are particularly valuable in monitoring long-term adverse events, (e.g., unresolved ongoing adverse events, and new treatment related adverse events including limb amputation for ulcers that do not heal).

If a subject is being withdrawn from the trial, attempt to schedule an early termination visit at which the End of Study procedures are carried out (refer to Section 8.1.6). Complete procedures described therein and document the reason for the subject's withdrawal.

8.2 Efficacy Assessments

The efficacy assessments rely primarily on observation of the wound, in order to determine if it has healed. While complete epithelialization is the standard definition of healing, the definition used in this protocol conforms to the 2006 FDA Guidance on wound healing, which requires two additional observations of healing at two week intervals. Photographic images of healed wounds will be reviewed by an independent expert in wound healing. Wounds that reopen (or re-ulcerate) after confirmed closure are also of interest, with the assessments in this case consisting of single observations. Patient reported outcomes are also recorded in order to evaluate the impact of a healed, or unhealed wound, on the subject's quality of life.

8.3 Safety and Other Assessments

Safety is evaluated at each visit by examination of the lower extremity and through both spontaneous and elicited reporting of adverse events.

8.4 Adverse Events and Serious Adverse Events

8.4.1 Definition of Adverse Events (AE)

An Adverse Event is any untoward medical occurrence temporally associated with the use of an investigational medicinal product, whether or not considered causally related to that product. An AE can be any unfavorable and unintended sign (for example, an abnormal laboratory finding), symptom, or disease. The Investigator, or his/her designee, will document AEs. AE data will be entered onto the appropriate source and electronic case report form (eCRF). Adverse events will be coded using Medical Dictionary for Regulatory Activities (MedDRA).

All AEs should be followed during the trial period. The Investigator should use his/her discretion in ordering additional tests as necessary to monitor the resolution of such events. Event outcome at resolution or at time of last follow up will be recorded as event resolved, resolved with sequelae, ongoing at discontinuation, or death. Investigators should continue to follow up events of concern outside of the trial per their standard of care. The trial database may be finalized in these cases with events noted as ongoing.

The Investigator should consider adverse events both as they relate to the investigational product and as they relate to the procedures involved in the trial such as debriding tissue. The Investigator is responsible for determining initial relationship and severity of adverse events.

All adverse events must be reported in the subject's source documents; AE associated with the index ulcer or related to the test article must be recorded on an Adverse Event Form regardless of whether or not they are considered to be related to the test article.

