3 OBJECTIVES AND ENDPOINTS

OBJECTIVES	ENDPOINTS	JUSTIFICATION FOR ENDPOINTS			
Primary					
To determine whether treatment of high grade DFU with standard care plus TTAX01 results in a higher probability of achieving complete wound closure over 26 weeks, compared with standard care alone.	Time from baseline to initial observation of healing, over 26 weeks, where healing has been confirmed at two consecutive visits each two weeks apart.	The endpoint complies with FDA guidance. Dropouts should be minimal during the first 26 weeks, but may increase thereafter. Analysis will use a Cox proportional hazard model			
Secondary					
To compare differences between treatment groups in proportions of wounds healed through 50 weeks	Proportions of wounds healed by Week 50	This endpoint provides insight into longer term benefits of the intervention			
To compare long term durability of closure between treatment groups	Proportions of wounds that re-ulcerate by Week 50	May provide insight into the quality of healing			
To compare limb preservation between treatment groups	Proportions of minor (portions of the foot) and major (ankle, above or below the knee) amputations following the initial procedure by Week 50	Each amputation risks loss of mobility, with consequent increased mortality			
To compare patient reported mobility (lower extremity function) between groups.	Total score on PROMIS Health Organization Neuro- QoL "Lower Extremity Function" at Study End.	The tool is an NIH validated measure of patient reported outcomes			
Safety					
To examine Quality of Life endpoints related to therapeutic intervention	Total score of quality of life assessment determined by Cardiff Wound Impact Schedule (CWIS) at Study End				
Proportion of subjects experiencing adverse events, by group	Spontaneously reported and elicited adverse events, coded in MedDRA				

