8.4.4 Time Period and Frequency for Event Assessment and Follow-Up

The occurrence of an AE or SAE may come to the attention of study personnel during study visits and interviews of a study participant presenting for medical care, or upon review by a study monitor.

All AEs including local and systemic reactions not meeting the criteria for SAEs will be captured on the appropriate case report form (CRF). Information to be collected includes event description, date of onset, clinician's assessment of severity, relationship to study product (assessed only by those with the training and authority to make a diagnosis) confirmed by the Principal Investigator, and date of resolution/stabilization of the event. All AEs occurring while on study must be documented appropriately regardless of relationship.

Any medical condition that is present at the time that the participant is screened will be considered as baseline medical history and not reported as an AE. However, if the study participant's condition deteriorates at any time during the study, it will be recorded as an AE.

Changes in the severity of an AE will be documented to allow an assessment of the duration of the event at each level of severity to be performed. AEs characterized as intermittent require documentation of onset and duration of each episode.

The Investigator will record all reportable events with start dates occurring any time after informed consent is obtained until the final study visit. At each study visit, the Investigator will inquire about the occurrence of AE/SAEs since the last visit. Event outcome at resolution or at time of last follow up will be recorded as "event resolved", "resolved with sequelae", "ongoing at discontinuation", or "death".

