8.4.5 Adverse Event Reporting

Disease Related Events expected in this population (angina, neuropathy, nephropathy, urinary tract infection, erectile dysfunction, retinopathy, hypoglycemic events) may be reported by the Investigator if they differ in nature or frequency from what is expected, or if they appear to have a causal relationship to the test article. All adverse events must be reported in the subject's source documents, and recorded on an Adverse Event Case Report Form regardless of whether or not they are considered to be related to the test article.

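### The adverse event recording rules in 8.4.1, 8.4.4 and 8.4.5 conflict, so comparability of the by-group proportion with non-serious AEs is not assured in this open-label trial

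*Protocol*

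**What the plan says.** Section 3 lists as a safety endpoint "Proportion of subjects experiencing adverse events, by group". Section 9.4.4 plans AE tables by system organ class and preferred term, with severity, frequency and relationship.

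Three sections govern what is recorded:

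- **8.4.1** states without limit that "AE data will be entered onto the appropriate source and electronic case report form (eCRF". Its last sentence requires all AEs in source documents and then adds, for the form, "AE associated with the index ulcer or related to the test article must be recorded on an Adverse Event Form". That sentence closes by saying that relation to the test article does not matter, although it has just used that relation as a criterion.
- **8.4.4** is broad: "All AEs including local and systemic reactions not meeting the criteria for SAEs will be captured on the appropriate case report form (CRF", and "All AEs occurring while on study must be documented appropriately regardless of relationship". Recording runs from consent to the final study visit.
- **8.4.5** opens with a list of events expected in diabetes, including angina, nephropathy, urinary tract infection and hypoglycemia. These "may be reported by the Investigator if they differ in nature or frequency from what is expected", or if a causal link to the test article appears. Its last sentence then requires all AEs to be "recorded on an Adverse Event Case Report Form regardless of whether or not they are considered to be related to the test article".

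Section 8.4.6 requires every SAE to be reported, attributable or not. Section 6.3 states that site staff are not blinded.

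**The concern.** A site cannot follow all of these sentences at once, and nothing says which prevails. Under the last sentence of 8.4.1, a site could keep non-serious, non-ulcer, unrelated events in source documents. Under the first sentence of 8.4.5, it could leave out ordinary disease-related events.

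Both sentences use relation to the test article as a trigger for recording. A control subject never receives the test article, so that trigger can operate in one arm only, and unblinded staff judge it. If sites apply these sentences, capture can depend on the arm, and the by-group AE proportion inherits that dependence. An analysis plan cannot repair this afterwards, because events never entered in the eCRF are not in the database.

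**Working it through.** The protocol states no AE rate, so there is no figure to reproduce. The check has two parts: a reading of the text, and an illustration on assumed rates.

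**1. The sentences applied to the same events**

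| Event | 8.4.1, last sentence | 8.4.5, first sentence | 8.4.4; 8.4.5, last sentence; 8.4.1, general sentence |
|---|---|---|---|
| Non-serious index-ulcer AE, either arm | Form mandatory | Not addressed | CRF |
| Ordinary urinary tract infection, control arm | Form not named | Optional, no trigger met | CRF |
| Same, TTAX01 arm, judged unrelated | Form not named | Optional, no trigger met | CRF |
| Same, TTAX01 arm, judged related | Form mandatory | Trigger met | CRF |
| Other non-serious, non-ulcer, unrelated AE | Form not named | Not addressed | CRF |
| Any SAE | Covered by 8.4.6 | Covered by 8.4.6 | Covered by 8.4.6 |

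The second and fourth rows show the asymmetry: the same clinical event can become recordable in the TTAX01 arm through a judgement that is not available in control. The last column treats the arms alike.

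**2. When a conflict of rules biases the arm contrast**

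All rates here are assumptions. Let A be the proportion with an index-ulcer AE, B the proportion with any other AE (independent of A), and c the share of those other AEs that reaches the form. Then

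P(any recorded AE) = 1 − (1 − A)(1 − B·c).

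With equal true rates in both arms, the false difference is (1 − A)·B·(c_TTAX01 − c_control). Take A = 0.30 and B = 0.30, 0.50, 0.70.

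| B | All AEs recorded (c = 1) | Other AEs not recorded (c = 0) | Half the sites on each rule, both arms | False difference, c = 1 vs 0.8 | False difference, c = 1 vs 0.5 |
|---|---|---|---|---|---|
| 0.30 | 51% | 30% | 40.5% | 4.2 points | 10.5 points |
| 0.50 | 65% | 30% | 47.5% | 7.0 points | 17.5 points |
| 0.70 | 79% | 30% | 54.5% | 9.8 points | 24.5 points |

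Worked example for B = 0.30: 1 − 0.70 × 0.70 = 0.51; with c = 0.8, 1 − 0.70 × (1 − 0.24) = 0.468; the difference is 0.70 × 0.30 × 0.20 = 0.042.

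Two things follow. The choice of rule moves the level of the endpoint (by 21 to 49 points on these assumptions). A mixture of rules across the roughly 23 sites, applied alike in both arms, leaves the contrast at zero. A false difference needs capture to differ by arm, and the test-article triggers are a route by which it can.

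**The case against.** The weight of the text is on one rule. Section 8.4.4, the last sentence of 8.4.5, the general sentence in 8.4.1 and the screening instructions in 8.1.1 all put AEs on the CRF or eCRF. The last sentence of 8.4.1 does not contain the word only, contradicts itself, and can be read as a minimum for one form. Section 8.4.4 also treats conditions present at screening as medical history unless they deteriorate, which would often cover neuropathy, nephropathy and retinopathy. The eCRF completion guidelines mentioned in 10.1.9.1 may settle practice. No AE hypothesis is stated in 9.1. An excess of related events in the TTAX01 arm would not flatter the product, and Section 2.2 reports no AEs attributable to TTAX01 among 32 Phase 2 subjects.

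Most of this is fair, and it limits the point. It does not remove it. Hypoglycemia and urinary tract infection remain ambiguous, the guidelines are not shown, and the protocol does not rank its sentences. The narrow reading also has some support elsewhere: in 8.1.4, 8.1.5 and 8.1.7, medication given for AEs is entered in the eCRF only for SAEs and for AEs judged related. That rule concerns medications and not the AEs themselves, but a site could take it as a guide.

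A reader might go further and infer that the AE proportions will not be comparable between arms, that non-ulcer events as a class will be lost, or that serious systemic signals will be missed. The documents do not support this. Site-to-site differences alone change the level and add noise. Related non-ulcer events stay under the last sentence of 8.4.1. SAEs are reported whatever the cause, and laboratory shift tables are planned.

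**Conclusion.** The contradiction is in the current text, and the two narrower sentences contain triggers that can be met only in the TTAX01 arm and are judged by unblinded staff. Comparability of the by-group proportion with non-serious AEs is therefore not assured. The text proves no more than that. The direction is not fixed either: a relatedness trigger would add events to the TTAX01 arm, while optional reporting of expected events can lose them in either arm.

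The size cannot be computed from the document. The figures in the table rest entirely on assumed AE rates, independence and capture shares, and show only how the mechanism works. The practical effect could be nil if all sites already follow 8.4.4. It is worth correcting because unrecorded events cannot be recovered at analysis.

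**What to change.** Apply the all-AE rule of 8.4.4 throughout: every AE in both arms, from consent to the final visit, goes on the AE CRF regardless of cause, relation to the index ulcer, or whether it is expected in diabetes. Rewrite the last sentence of 8.4.1 to say the same. Delete the permissive sentence at the start of 8.4.5, or state that it concerns expedited reporting only and not CRF entry. Align the eCRF completion guidelines and notify sites.

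Most of the rule is already written, so the cost is a text amendment, a guideline update and a site notice. The one small downside is more AE entries per subject.
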